## 2.9 Protocol Deviations

Protocol deviations will be collected only for the preliminary analysis. A listing of the potential protocol deviations will be prepared by Assign Data Management and Biostatistics GmbH using information from the eCRF documentation and monitoring reports. These protocol deviations will be classified into major or minor protocol deviations based on their possible impact on the study results in a Blind Data Review Meeting (BDRM) prior to the preliminary analysis attended by Assign Data Management GmbH and Themis Bioscience GmbH (sponsor).

Major protocol deviations will include but are not limited to the following:

- Subjects with any confirmed immunosuppressive or immunodeficient condition, including human immunodeficiency virus (HIV), hepatitis A, B or C infection or a family history of congenital or hereditary immunodeficiency
- Subjects who received the wrong or no IMP
- Subjects who received less than the protocol-defined number of vaccinations
- Subjects who received a wrong dose other than they were randomized to
- Subjects who entered the study even though they did not satisfy the entry criteria
- Subjects with substantial time window violations on vaccination visits
- Subjects who received a forbidden prior or concomitant medication
  - Immunosuppressive drugs: Use of corticosteroids (excluding topical preparations) or immunosuppressive drugs within 30 days prior to first IMP administration, or anticipated use during the trial
  - Treatments with non-study licensed vaccines within 4 weeks prior to first study vaccination until the end of the treatment period (day 56)
  - Receipt of blood products or immunoglobulins within 120 days prior to the Screening Visit or anticipated receipt of any blood product or immunoglobulin before completion of the treatment period (day 56)
- Further protocol deviations that could impact immune response that have not been described above

These criteria for potential protocol violation are identified at the time of planning the study. However, during the course of the trial unforeseen events may occur or new scientific knowledge may become available, therefore final decisions on whether any protocol violation could impact immune response and thus lead to exclusion from the per-protocol (PP) population will be made by the sponsor on a case by case basis in a blinded manner (and prior to study unblinding).

All protocol deviations will be listed in the analysis and described in the Clinical Study Report (CSR).

In case of unexpected changes or further protocol deviations documented after the BDRM, it may be discussed in a second DRM prior to database closure which analyses may be repeated for the final analysis.

## 2.10 Medical Coding

Adverse events, medical history and concomitant procedures will be coded using MedDRA in the most current version. Concomitant medications and vaccination history will be coded using WHO Drug Reference List and Anatomical Therapeutic Chemical (ATC) Classification System in the most current version. The used dictionary versions will be indicated in the respective tables and listings.

## 2.11 Analysis Populations

### 2.11.1 Safety Population

All safety analyses will be based on the safety population, defined as participants who entered into the study and received at least one IMP administration. All analysis based on the Safety Population will be carried out using the actual treatment received.

Possible issues with wrong treatment and assignment of subjects to actual treatment group will be discussed in the DRM. In general, this assignment will be done in a conservative way to not bias the safety results towards MV-ZIKA-RSP. If a subject in the high dose group receives a low dose, the subject will be analysed in the low dose group, for example.

### 2.11.2 Modified Intent-to-Treat (mITT) Population

The secondary immunogenicity analyses will be based on the modified ITT population. The modified intent-to-treat (mITT) analysis population is defined to include all participants randomised who receive at least one IMP administration. Participants will be analysed according to the treatment group they had been allocated to, rather than by the actual treatment they received.

When no subjects received wrong treatment, mITT and Safety population do not differ and tabulations will only be done for safety population.

### 2.11.3 Per-Protocol (PP) Population

The immunogenicity analysis will be assessed primarily on the per-protocol (PP) population. The PP population includes participants without protocol deviations that could impact immune response. Examples that may lead to exclusion from the PP population are provided here:

- Immunosuppressive drugs: Use of corticosteroids (excluding topical preparations) or immunosuppressive drugs within 30 days prior to first IMP administration, or anticipated use during the trial.
- Participants with any confirmed immunosuppressive or immunodeficient condition, including human immunodeficiency virus (HIV), hepatitis A, B or C infection or a family history of congenital or hereditary immunodeficiency
- Participants who received the wrong or no IMP

These criteria for potential protocol violation are identified at the time of planning the study. However, during the course of the trial unforeseen events may occur or new scientific knowledge may become available, therefore final decisions on whether any protocol violation could impact immune response and thus lead to exclusion from the PP population will be made by the sponsor on a case by case basis in a blinded manner (and prior to study unblinding at the preliminary analysis). Sample testing issues may also lead to exclusion from the PP population for particular time points.

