## 2. GENERAL CONSIDERATIONS

### 2.1 Conduct of Analysis

A preliminary analysis including safety and immunogenicity data will be performed after all participants completed Visit 3 (day 56) and therefore terminated the treatment period of the study. This analysis will cover the primary safety endpoint (adverse events up to day 56) and some immunogenicity endpoints. The purpose of this analysis is to provide highly valuable data for further zika vaccine development.

Results from this preliminary analysis will not have any impact on the study design or the participants during the follow up period of the study.

The final analysis will be conducted after the last subject completed the Post Treatment Safety Follow-Up and the database was closed. All data of the study will already be available at the preliminary analysis except the Adverse Events and Prior/Concomitant Medication data from Visit 4 (Day 182). Thus, only Adverse Events and Prior/Concomitant Medication data will be analyzed at the final analysis. If unexpected changes occur e.g. in the immunogenicity data, analyses may also be repeated at the final analysis.

SAP update (Final 2.0): Due to the covid pandemic, at the time of analysis of the samples, laboratory capacities were limited, and no results were available. For this reason, immunogenicity analysis was not conducted for the preliminary analysis. Instead, the immunogenicity analysis will be done as described in Section 5 for the final analysis only.

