## 2.4 Blinding and Randomization

### Blinding:

As this study will be conducted in an observer-blinded manner, unblinded study team members responsible for randomisation, monitoring (unblinded monitor) and preparation of IMP, will otherwise not be involved in the conduct of the study.

All participants, the investigator and site personnel performing study related assessments, as well as the sponsor's representatives involved in the monitoring (blinded monitor) and conduct of the study, will be blinded to treatment assignment.

Besides one set of randomisation envelopes, the site will receive an additional set of emergency envelopes stored in the ISF for unblinding purposes. As the knowledge of the subject's treatment might become mandatory (e.g. in case of emergency) the investigator has the possibility to open the emergency envelope, identified with the subject's randomisation number, and unblind the subject.

The investigator and site personnel assessing AEs, all participants, as well as one of the sponsor's representatives involved in the monitoring and conduct of the study will be blinded to which vaccine was administered. Only the unblinded monitor, site personnel performing randomisation and preparation of IMP will be unblinded.

The primary endpoint as well as most of the secondary endpoints will be covered in the preliminary analysis after Day 56 and only a safety follow-up phone call will be performed after Day 56. The sponsor personnel and ADMB team, involved in generation and review of the preliminary analysis and underlying data management activities, will be unblinded after the Blind Data Review Meeting (Section 2.9) and database snapshot for preliminary analysis.

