### 5.2 Derivations and Definitions

- For final analysis all time points, including Visit 1 (Day 0), Visit 2 (Day 28) and Visit 3 (Day 56) will be analyzed.
- Seroconversion rate for anti-zika-rsp VNT titers is defined as proportion of subjects achieving anti-zika-rsp VNT titers  $\geq 20$  at a certain time point.

- Seroconversion rate for anti-zika-rsp ELISA titers is defined as 4-fold increase over baseline (Visit 1 –Day 0). If no Visit 1 (Day 0) sample is available, no seroconversion will be determined.
- For MV ELISA, Zika ELISA, NT and T-Cell an analysis of positive versus negative values is planned. Since such a definition could not be discussed and communicated with the central laboratory at the time of generation of this SAP, details about used limits will be shown as footnotes in the corresponding tables and explained in the Clinical Study Report.
- For the different immunogenicity parameter there are different lower limit of quantification (LLOQ). [redacted]
  - In data listings, the original reported value “<LLOQ” will be displayed.
  - For calculations (GMT, median...) the half of the true LLOQ value will be used for such values.
  - If another unexpected value is reported as LLOQ in the data than mentioned here, the half value of the reported LLOQ will be used for the calculations.
- For the different immunogenicity parameters there are different upper limits of quantification (ULOQ) [redacted]
  - In data listings, the original reported value “>ULOQ” will be displayed.
  - For calculations (GMT, median...) the ULOQ value will be used for such values.
  - If another unexpected value is reported as ULOQ in the data than mentioned here, this ULOQ value will be used for calculations.
- For analysis using interval-censored data an interval will be defined for every observation. Observations between LLOQ and ULOQ will be handled as interval with left limit and right limit being the observed value. For values <LLOQ the interval will be left-censored with the LLOQ as right limit. For values >ULOQ the interval will be right-censored with the ULOQ as left limit.

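### With immunogenicity moved past the Day-56 unblinding, the SAP's blinding statement does not cover sample-testing exclusions, positivity limits or late per-protocol changes

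*Combined protocol and SAP*

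**What the plan says.** - **SAP 2.11.3** makes the PP set primary for immunogenicity. The sponsor judges case by case whether a protocol violation could affect immune response, "in a blinded manner (and prior to study unblinding at the preliminary analysis). Sample testing issues may also lead to exclusion" from the PP set at particular time points. The sentence on sample testing carries no criteria, no decision time and no blinding condition. Protocol 12.5.3 reads the same way.
- **SAP 2.1**, in the Final 2.0 update, reports that "laboratory capacities were limited, and no results were available" and that "immunogenicity analysis was not conducted for the preliminary analysis". It continues: "Instead, the immunogenicity analysis will be done as described in Section 5 for the final analysis only".
- **SAP 2.4** states that the sponsor personnel and the statistics and data management team working on the preliminary analysis "will be unblinded after the Blind Data Review Meeting (Section 2.9) and database snapshot for preliminary analysis".
- **SAP 2.9** classifies deviations at the Blind Data Review Meeting before the preliminary analysis. If unexpected changes or further deviations appear later, "it may be discussed in a second DRM prior to database closure which analyses may be repeated for the final analysis".
- **SAP 5.2** plans positive/negative analyses for measles ELISA, Zika ELISA, NT and T cells but gives no limits: "Since such a definition could not be discussed and communicated with the central laboratory at the time of generation of this SAP". The limits are to appear in table footnotes and be explained in the study report.
- **SAP 2.6** compares positivity and seroconversion rates between groups with the Fisher-Freeman-Halton test.

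**The concern.** The PP wording fits a plan in which titres were analysed at Day 56, so that one blind meeting could settle everything before codes were released. Once the assays moved to the final analysis, that meeting could no longer settle matters that depend on laboratory results. The blinding section and the PP section were not adapted.

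Following the SAP as written, people who already hold treatment codes may take part in deciding which samples are invalid and where the line between positive and negative falls. With 8 to 14 participants per arm, either choice can change a between-group comparison. The study report could then describe its primary immunogenicity set as defined blind when the plan did not ensure this for sample-level exclusions.

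**Working it through.** The plan states no power or alpha figure to reproduce on this point. The check is the order of events, followed by illustrations of size.

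**1. Order of events**

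| Decision | Information needed | Secured before unblinding? |
|---|---|---|
| PP exclusion for a deviation (forbidden drugs, conditions, wrong or no product) | Case report form and monitoring data | Yes, at the blind meeting (SAP 2.9) |
| PP exclusion of a time point for a problem found in testing | Assay results | No: none existed at the preliminary analysis (SAP 2.1) |
| Positivity limits, four assays | Laboratory input | No: still open in an SAP that speaks of the preliminary analysis in the past tense (SAP 5.2, 2.1) |
| PP change reopened at the second meeting | Later deviations or data changes | No: that meeting is not stated to be blind (SAP 2.9) |

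**2. Which results are exposed**

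- Positivity limits feed the positivity tables in both the mITT and PP sets.
- Sample exclusions and late PP changes feed the PP geometric mean titres, seroconversion and positivity.
- VNT seroconversion (titre of at least 20) and Zika ELISA seroconversion (4-fold rise) have fixed cut-offs in SAP 5.2.
- The primary endpoint, adverse events to day 56, uses none of these choices.

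**3. Largest shift from one exclusion**

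Dropping one positive from k/n changes the rate by k/n − (k−1)/(n−1) = (n−k)/[n(n−1)]. This is largest at k = 1, where it equals 1/n. Dropping one negative has the same maximum. With the arm sizes in SAP 2.4:

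- A and B: 1/14 = 7.1 points
- C: 1/12 = 8.3 points
- D: 1/8 = 12.5 points

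**4. Effect of one exclusion on a test (response counts assumed)**

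Pairwise two-sided Fisher test, A against D: 8/14 vs 1/8 gives p = 0.074. Removing the one positive placebo sample gives 8/14 vs 0/7, p = 0.018. This is not the planned test.

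For the planned four-group test, keep A = 8/14, change D from 1/8 to 0/7, and vary B over 1 to 8 of 14 and C over 1 to 7 of 12. That is 8 × 7 = 56 patterns:

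- 21 move from above 0.05 to at or below it;
- 18 are already at or below 0.05 and stay there;
- 17 stay above 0.05.

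So 21 of the 21 + 17 = 38 patterns that start above 0.05 cross it. With B = 6/14 and C = 5/12, p falls from 0.289 to 0.085 and does not cross.

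**5. Effect of choosing a limit with codes known (number of candidate limits assumed)**

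With no group difference, arms of 14/14/12/8, exact Fisher-Freeman-Halton p-values and 20,000 permutations, the chance of p ≤ 0.05 for one assay at one visit is:

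| Limit | Chance |
|---|---|
| One fixed in advance (24/48 positive) | 5.1% |
| Best of 3 (12, 24 or 36 positive) | 12.6% |
| Best of 5 (8, 16, 24, 32 or 40 positive) | 18.3% |
| Any giving 5 to 43 positive | 38.7% |

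The Monte Carlo standard error at 5% is √(0.05 × 0.95 / 20,000) = 0.15 points. The last three rows assume that the limit with the smallest p-value is picked, which is the worst case.

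**The case against.** A reader might infer that the PP population as a whole has lost its blinded definition. The documents do not support that. The blinding statement concerns protocol violations, which need no titres and are classified at the blind meeting before the preliminary analysis. For those exclusions it can still be true.

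A reader might also infer that unblinded staff will set the positivity limits. SAP 5.2 says only that the definition awaited discussion with the central laboratory. SAP 2.4 unblinds only the sponsor and statistics staff involved in the preliminary analysis, and treatment is not among the label items listed in protocol 8.11.4. The laboratory could set limits from assay validation alone. This stands as a limit on the point: the SAP permits treatment-aware choices but does not prescribe them. It also does not require the laboratory route, and the documents do not say whether laboratory staff are blinded.

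The SAP also uses the plain term data review meeting loosely (in 2.11.1, for instance), and 2.9 has the second meeting discuss which analyses to repeat. The missing word blind is therefore weak evidence by itself. What stands is that no text makes that meeting blind if PP membership is reopened there.

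Finally, the mITT tables limit the damage. SAP 5 and 7.1 plan every immunogenicity table for mITT and repeat it for PP, and sample-testing exclusions are described for PP only. A selective exclusion would show as a difference between the two sets. This protection is real, but it does not extend to positivity limits, which would be the same in both.

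**Conclusion.** The gap is real but narrow. After the move in SAP Final 2.0, the statement in 2.11.3 does not secure blinding for time-point exclusions due to sample testing, for the four positivity limits, or for any PP change reopened at the second meeting. Deviation-based PP membership, the VNT and Zika ELISA seroconversion cut-offs and the primary safety endpoint are unaffected.

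The size is bounded by 7.1 to 12.5 points per exclusion. In an example chosen to be adverse, with the only positive placebo sample dropped, the planned test crossed 0.05 in 21 of 56 patterns and did not in 35. These counts, and the numbers of candidate limits, are assumptions; they show what the plan allows, not what happened. The conclusion rests on unblinding having followed SAP 2.4. Because immunogenicity is secondary in a 48-participant Phase I trial without a formal sample size calculation, this should be fixed but does not undermine the main result.

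**What to change.** Amend SAP 2.4, 2.9, 2.11.3 and 5.2 as follows.

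1. Before assay results are merged with treatment codes, the laboratory and reviewers without code access fix and document, in a dated and signed memo, the sample-validity exclusions by time point, the positivity limits for NT, Zika ELISA, measles ELISA and T cells, and any late PP change.
2. State that the second data review meeting is blind for these decisions.
3. Keep the existing statement on blinded PP decisions, but limit it to exclusions based on protocol deviations.
4. Name the planned mITT tables, with no sample-level exclusions, as the sensitivity analysis for the PP results.

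The cost is SAP wording, a short memo and restricted access to codes while the assay data are reviewed. Reviewers must be people not unblinded at the preliminary analysis. No new data are needed. If any of these choices has already been made by someone with access to codes, the study report should say so and show the results with and without it.

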## 2.12 Subject Data Listings

All treated subjects will be included in listings if not stated otherwise (e.g. subject overview listings, screening failure listing). Data listings will include the subject number as identifier (and parameter and/or visit if available) and will be sorted by treatment group, subject number and parameter and/or visit if available (in this order). Columns that indicate the treatment group will be shown in all listings.

## 2.13 Columns in Tables

Every treatment group has its own column in the analysis and an additional total column will be added. For OV tables, where all subjects are shown, there is an additional column with subject not randomized.

## 2.14 Changes in the Conduct of the Study or Planned Analysis

No changes to the statistical analysis as compared to CSP are planned.

### 3. OVERALL STUDY INFORMATION

For visit attendance and study status the safety population is used. For the other OV tables all subjects are used.

#### 3.1 Data points

The following information will be analyzed descriptively and corresponding details on the subject level will be provided in data listings:

- Subject overview (screened, randomized, 1st/2nd IMP administered, study populations...)
- Visit attendance
- Protocol deviations
- Study status (incl. drop-outs and reason)
- Screening failures

For details on table and listing content, see Section 7.

#### 3.2 Derivations and Definitions

Details about study population can be found in Section 2.11.

### 4. BASELINE EVALUATION

Baseline analysis will be presented for the Safety, mITT population and for the PP population. In case populations do not differ, tabulations will not be repeated.

#### 4.1 Data points

The following information will be analyzed descriptively and corresponding details on the subject level will be provided in data listings:

- Demographic information (age, sex, race)
- System-based Physical examination (will be listed only)
- Vaccination history (by ATC level 3)
- Virology (will be listed only)
- Medical history
- Prior and concomitant medications
- Pregnancy Test (will only be listed)
- Concomitant Procedure (will only be listed)
- Vital Signs at screening

For details on table and listing content, see Section 7.

## 4.2 Derivations and Definitions

Medications stopped clearly prior (<) to Day 0 (Visit 1) will be considered prior medications, all other medications are considered to be concomitant. Medications with a missing or incomplete stop date where it cannot clearly be decided if the stop date was before or after Day 0 will be considered concomitant.

## 5. IMMUNOGENICITY ANALYSIS

The immunogenicity analysis will be performed for the mITT and PP population. All tables will be presented by treatment group and overall. Data from the early termination visit or unscheduled visits will be listed only and will not be shown in summary tables by time point.

